6.4. Rescue Medications, Treatments, and Procedures

The plan for managing psychiatric emergencies includes:

- A detailed therapist manual, and training for all study therapists on procedures in the manual for handling potential adverse events including agitation, hallucinations, anxiety, and other intense psychological reactions.
- The two-person therapist team that will be with the participant for the entire medication dosing session will include a licensed therapist or physician with training in psychiatric emergencies and adverse effects of psychedelics.
- A psychiatrist team member will be involved in screening and evaluation of all participants.
- A physician with training in psychiatric emergencies and adverse effects of psychedelics will be immediately available on site for the medication dosing days.
- A psychiatrist team member will be immediately available to assess any participant noted by study staff to have a significant change in mood or suicidality.
- In the event of a psychiatric emergency, the Harborview Medical Center Psychiatry Emergency Services in the next building is available 24 hours a day, with on-site psychiatrists and nurse practitioners.
- The PI may prescribe a designated rescue medication in the event of symptoms that require it during or after the medication dosing session. Study therapists who have performed first-line and second-line interventions (that do not involve medications) will have the ability to contact the PI by phone, who is available to assess patients within 20 min during every medication session. If a patient does have an adverse reaction that requires a rescue medication, participants will be monitored for up to 2 hours beyond the required 6 hour duration of the session. If at the end of that period that participant requires further, [name] (PI) will consult with the attending psychiatrist on call at Harborview Medical Center.

If participants experience or report on any adverse effects or if the research staff feels that at the end of testing, that the participant has any adverse effects, participants will be able to remain until effects wear off (likely only for a short period) and medical assistance will be offered. Participants will be free to withdraw from the study whenever they wish. In addition, if any participant presents with an adverse reaction to the psychopharmacological agent as reported by them or assessed by a member of the research team, we will discontinue the study and call for medical assistance

6.5. Safety Plan for Suicidality:

During all study visits a study investigator with clinical training will assess the participant's well-being – responses, intent, plan, etc. while administering the C-SSRS (Columbia Suicidality Severity Response Scale). If these procedures result in any serious concerns on the part of the investigator, they will either ask the participant to meet with or call the PI or escort the participant to the

Page 31 Version 1.16, July 18, 2022

emergency room. If necessary, they will also call the participant's treating clinician and/or their emergency contact. As part of the consent, participants are required to designate an emergency contact person and provide their treating clinician's contact information. We will ask the treating clinician for their local plan for such emergencies so the study team can follow this plan should an emergency situation arise.

7. Payments for Participation (Economic Considerations)

Participants will not be paid for their participation. Expenses of participating in the study, such as parking will be covered by the study.

8. Assessment of Safety

- 8.1. Specification of Safety Parameters
- 8.1.1. Definition of Adverse Events (AE)

Adverse events (AEs) are defined any untoward, physical, social, economic, or psychological occurrence affecting human subjects in research. An AE can be any unfavorable or unintended event including abnormal laboratory finding, symptom, reaction, or disease. An AE does not necessarily have a causal relationship with the research, or any risk associated with the research, the research intervention, or the assessment. Adverse events involve subjects only.

8.1.2. Definition of Serious Adverse Events (SAE)

In addition to grading the adverse event, adverse events are evaluated to determine whether they meet the criteria for a Serious Adverse Event (SAE). An SAE is defined as death; a life threatening experience; inpatient hospitalization (for a person not already hospitalized); prolongation of hospitalization (for a patient already hospitalized); persistent or significant disability or incapacity; congenital anomaly and/or birth defects; or an event that jeopardizes the participant and may require medical, surgical, or other intervention to prevent one of the preceding conditions (FDA, 21 CFR Part 312). An adverse event is considered serious if it:

- is life-threatening
- results in in-patient hospitalization or prolongation of existing hospitalization
- results in persistent or significant disability or incapacity
- results in a congenital anomaly or birth defect OR
- results in death
- based upon appropriate medical judgment, may jeopardize the subject's health, and may require medical or surgical intervention to prevent one of the other outcomes listed in this definition, or
- adversely affects the risk/benefit ratio of the study

An adverse event may be graded as severe but still not meet the criteria for a Serious Adese Event. Similarly, an adverse event may be graded as moderate but still meet the criteria for an SAE. It is important for the PI to consider the grade of the event as well as its "seriousness" when determining whether reporting to the IRBs and the Medical Monitor is necessary.

8.1.3. Definition of Unanticipated Problems (UP)

An unexpected adverse event is one that is not listed in the current Investigators Brochure for Psilocybin, assisted psychotherapy produced by MAPS or an event that is by nature more specific or more severe than a listed event.

Such an event is unlikely because as of 01 December 2016, with over 1000 individuals exposed to Psilocybin in controlled research settings, there have been no unexpected drug-related SAEs to date and expected SAEs have been rare and non-life threatening.

8.1.4. Classification of an Adverse Event

The following scale will be used in grading the severity of adverse events noted during the study:

- 1. Mild adverse event (does not affect patient activity)
- 2. Moderate adverse event (mild disruption in usual activity)
- 3. Severe (major disruption in usual activity)

8.2. Time Period and Frequency for Event Assessment and Follow-Up

Adverse events will be reviewed with subjects weekly from the time of preparation visit 1 through primary outcome collect at 4 weeks. Information will be assessed in-person and during weekly phone calls. Adverse events or unanticipated problems involving risks to subjects or others will be reported to the HIC or HSC within 48 hours of it becoming known to the investigator, using the appropriate forms found on the website.

8.3. Reporting Procedure (Adverse Events)

The investigator will report the following types of adverse events:

- a. serious and unanticipated and possibly, probably, or definitely related events;
- b. anticipated adverse events occurring with a greater frequency than expected;
- c. other unanticipated problems involving risks to subjects or others.

8.4. Study Halting Rules

The Medical Monitor or the Principal Investigator has the right to discontinue this study at any time. If the trial is prematurely terminated, the Primary Investigator is to promptly inform the study participants and will assure appropriate therapy and follow- up. If the trial or study is prematurely discontinued, all procedures and requirements pertaining to retention and storage of documents will be observed. All other study materials will be treated in accordance with federal and state regulations.

8.5. Attribution of Adverse Events

Adverse events will be monitored for each subject participating in the study and attributed to the study procedures / design by the principalinvestigator according to the following categories:

- a. Definite: Adverse event is clearly related to investigational procedures(s)/agent(s).
- b. Probable: Adverse event is likely related to investigational procedures(s)/agent(s).
- c. Possible: Adverse event may be related to investigational procedures(s)/agent(s).
- d. Unlikely: Adverse event is likely not to be related to the investigational procedures(s)/agent(s).
- e. Unrelated: Adverse event is clearly not related to investigational procedures(s)/agent(s).
- 8.7. Plan for Grading Adverse Events: The following scale will be used in grading the severity ofadverse events noted during the study:
 - a. Mild adverse event
 - b. Moderate adverse event

c. Severe

8.8. Plan for Determining Seriousness of Adverse Events:

Serious Adverse Events: In addition to grading the adverse event, the PI will determine whether the adverse event meets the criteria for a Serious Adverse Event (SAE). An adverse event is considered serious if it results in any of the following outcomes:

- a. Death;
- b. A life-threatening experience in-patient hospitalization or prolongation of existing hospitalization;
- c. A persistent or significant disability or incapacity;
- d. Any other adverse event that, based upon appropriate medical judgment, may jeopardize the subject's health, and may require medical or surgical intervention to prevent one of the other outcomes listed in this definition.

An adverse event may be graded as severe but still not meet the criteria for a Serious Adverse Event. Similarly, an adverse event may be graded as moderate but still meet the criteria for an SAE. It is important for the PI to consider the grade of the event as well as its "seriousness" when determining whether reporting to the IRB is necessary.

8.9. Plan for reporting UPIRSOs (including Adverse Events) to the IRB.

The Principal Investigator will report the following types of events to the IRB: Any incident, experience or outcome that meets ALL 3 of the following criteria:

- 1.Is unexpected (in terms of nature, specificity, severity, or frequency) given (a) the research procedures described in the protocol-related documents, such as the IRB-approved protocol and informed consent document and (b) the characteristics of the subject population being studied; AND
- 2. Is related or possibly related to participation in the research (*possibly related* means there is a reasonable possibility that the incident, experience, or outcome may have been caused by the procedures involved in the research); AND
- 3. Suggests that the research places subjects or others at greater risk of harm (including physical, psychological, economic, legal, or social harm) than was previously known or recognized.
- 8.10. Unanticipated Problems Involving Risks to Subjects or Others (UPIRSOs) may be medical or non-medical in nature and include but are not limited to *serious, unexpected, and related adverse events* and *unanticipated adverse device effects*. *Please note* that adverse events are reportable to the IRB as UPIRSOs only if they meet all 3 criteria listed above.

These UPIRSOs/SAEs will be reported to the IRB using the appropriate forms. In the event that such events occur, Reportable Events (which are serious or life-threatening and unanticipated, or anticipated but occurring with a greater frequency than expected, and possibly, probably, or definitely related) or Unanticipated Problems Involving Risks to Subjects or Others that may require a temporary or permanent interruption of study activities will be reported immediately (if possible), followed by a written report to the IRB within 5 calendar days (in accordance with IRB Policy 710) of the Principal Investigator becoming aware of the event (using the appropriate forms) and to any appropriate funding and regulatory agencies.

All related events involving risk but not meeting the prompt reporting requirements

should be reported to the IRB in summary form at the timeof continuing review. If appropriate, such summary may be a simple brief statement that events have occurred at the expected frequency and level of severity as previously documented.

8.11. Plan for reporting adverse events to co-investigators on the study, research monitor(s), e.g., Protocol Review Committee (PRC), study sponsors, funding and regulatory agencies, and regulatory and decision-making bodies.

For the current study, the following individuals, funding, and/or regulatory agencies will be notified:

- a. All Co-Investigators listed on the protocol.
- b. Food and Drug Administration
- c. Study Funding and Sponsors

The investigator will apprise fellow investigators and study personnel of all UPIRSOs and adverse events that occur during the conduct of this research project throughregular study meetings, or via email as they are reviewed by the principal investigator.

The protocol's research study sponsors, funding and regulatory agencies, and regulatory and decision-making bodies will be informed of any Serious, Unanticipated and Related adverse events within 5 days (or within any contract or policy designated time period) of the event becoming known to the principal investigator.

The principal investigator will conduct a review of all adverse events upon completion of every study subject. The principal investigator will evaluate the frequency and severity of the adverse events and determine if modifications to the protocol or consent form are required.

8.12. Safety Oversight

The principal investigator in conjunction with the Medical Monitor will be responsible for monitoring the data, assuring protocol compliance, and conducting the safety reviews at the specified frequency, which must be conducted at aminimum of every 6 months (including when reapproval of the protocol is sought).

During the review process, the principal investigator (in collaboration with the Medical Monitor) will evaluate whether the study should continue unchanged, require modification or amendment, continue or close to enrollment. Either the principal investigator, the HIC, or the Medical Monitor have the authority to stop or suspend the study or require modifications. Likewise, the principal investigator will periodically review the collection, storage, and distribution practices associated with clinical data bank, and determine whether changes to enhance confidentiality and privacy are required. The research team will follow the University of Washington guidelines for attribution of adverse events andgrading the severity of adverse events (including determining whether the adverse event mediciteria for a Serious Adverse Event).

8.13. Clinical Monitoring

After administration of Psilocybin/placebo, participants will be checked regularly. A research team member will accompany the participants and be available at all times tocall for medical assistance if required. Procedures will be immediately stopped if participants request to stop or exhibit any sign of significant distress. The study therapists will have immediate access to the PI or a designated physician to

assess any problems, or to clear a participant for discharge from the research facility.

9. Statistical Considerations

9.1. Measures to Minimize Bias

9.1.1. Enrollment/Randomization/Masking Procedures

The necessary strict exclusion criteria for psilocybin interventions may limit generalizability of the findings. The influence of repeated testing in the crossover design will be minimized by modeling order effects in analyses, but some effects of practice may persist.

9.1.2. Evaluation of Success of Blinding

At the end of the randomized treatment, participants will be asked to fill out a 5 point Likert scale with the following options:

- -- I am positive I received psilocybin
- -- I think I received psilocybin
- --I cannot tell whether I received psilocybin or niacin (placebo)
- --I think I received niacin (placebo)
- -- I am positive I received niacin (placebo)

9.1.3. Source Documents and Access to Source Data/Documents

Paper source documents and research case books will be housed in restricted access files. Personally-identified information will be restricted to name, address, phone number, birthdate, social security numbers, dates of care, and will be kept by investigators in a separate file from the research data which will be coded using a unique subject identification.

9.1.4. Quality Assurance and Quality Control

The principal investigator is responsible for monitoring the data, assuring protocol compliance, and conducting the safety reviews yearly. During the review process, the principal investigator will evaluate whether the study should continue unchanged, require modification/amendment, continue or close to enrollment. Either the principal investigator or the IRB have the authority to stop or suspend the study or require modifications.

9.2. Statistical approach

The primary objective of this randomized trial is to compare the mean change from baseline MADRS among patients randomized to receive psilocybin to that among patients randomized to receive niacin. The time point of primary interest at which change will be assessed will be 4 weeks. Mean change between the two groups will be assessed with the two-sample t-test, or the Wilcoxon rank-sum test if distributional assumptions for the t-test are violated. The table below shows the minimum detectable assumed-true effect size (represented in standard-deviation units, or the difference in mean change divided by the common standard deviation) to observe a statistically significant difference (at the two-sided significance level of .05) with 80% and 90% power for a variety of total sample sizes.

Sample size	80% Power	90% Power
N=30	1.06 SD units	1.23 SD units
N=40	0.91 SD units	1.05 SD units
N=50	0.81 SD units	0.94 SD units

Based on the values in the above table, we will randomize 30 patients, as we hypothesize that an assumed-true effect size of 1.06 – 1.23 is achievable based on previous studies by [name] and Davis and achieved effect sizes of 1.46 at 2 weeks at 1.69 at 6 weeks¹⁹ or 2.2 at 5 weeks.¹⁸ A sample size of N=30 will provide >90% power to detect a significant difference in the primary outcome between the psilocybin 25 mg vs niacin groups. Assuming a 15% drop-out rate of subjects in this study, we will enroll 36 subjects and assume 6 will not complete the study, so full enrollment in this study will be 36 with a target of 30 subjects completing the study.

The primary analysis will be done using the intent-to-treat principle. Randomization will be done using a permuted block design with randomly selected block sizes.

Key secondary endpoints include those listed below, and a hierarchical approach will be taken to the potential analysis of these endpoints. If the primary endpoint is statistically significant, then these secondary endpoints will be (potentially) formally compared in a hierarchical manner in the order listed below.

- 1. Mean change in burnout (Stanford Fulfillment index) from baseline to 4 weeks between the two groups
- 2. Mean change in symptoms of PTSD (PCL5) from baseline to 1 week and 4 weeks between the two groups.

These secondary endpoints will be compared between groups as described above. At the first endpoint that is not statistically significant (at the two-sided significance level of .05), all subsequent endpoints will be evaluated descriptively and not formally assessed in order to maintain the overall type I error rate of .05.

10. Ethics/Protection of Human Subjects

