3.1.6. Study Enrollment and Withdrawal

Participant Population – physicians and nurses with moderately severe symptoms of depression. Participants meeting study inclusion / exclusion criteria after careful screening and examination will be invited to participate and will be provided with all the information needed to provide an informed consent. We will recruit 30 adult participants (25 to 65 years) of both sexes with clinically significant symptoms of depression.

4. Participant Inclusion and Exclusion Criteria

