4.5. Participant Withdrawal or Termination

Participants may withdraw their consent for use of their data and/or terminate participation in the study at any moment during the study by calling the Principal Investigator or a member of the research team. To revoke authorization of the use and disclosure of Personal Health Information, the participant must follow-up the phone call by submitting a request in writing to the Principal Investigator. In this event, the Principal Investigator will indicate in the data base that consent from the participant is no longer active, and that data can no longer be used.

Page 24 Version 1.16, July 18, 2022

A participant may be withdrawn from the research for any of the following reasons:

- (1) A participant will be withdrawn if they become actively suicidal
- (2) A participant will be withdrawn if during the preparation visits, they show signs of severe personality disorder that was not evident in the screening visit.
- (3) A participant may be withdrawn if their withdrawal is in the best interests of either the participant or of the research (e.g., due to a medical condition making the procedures unsafe or any condition making interpretation of the results difficult).
- (4) A participant may be withdrawn if they are unable to comply with study visits (e.g., they miss their preparation visits without explanation).

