Findings of pregnancy, active cardiac medical issues, abnormal liver function, abnormal renal function, or abnormal blood counts, and any lab indicating an undiagnosed illness would exclude a participant from moving on to the preparation 1 visit. When screening requirements have been met, participants will have a visit with the PI and/or key study personnel in which the study, the scheduling and the procedures will be reviewed. All participants' questions will be answered prior to obtaining an informed consent.

After providing informed consent, the participant will complete initial measures. Note that randomization to the psilocybin or control (niacin) treatment groups will occur at the end of visit 2.

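### Section 9.2 claims over 90% power for N=30 without naming an effect; at its own assumed effect of 1.06 to 1.23 SD, 30 analysed participants give 80% to 90%

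*Combined protocol and SAP*

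**What the plan says.** Section 9.2 compares mean MADRS change at 4 weeks by a two-sample t-test, "at the two-sided significance level of .05". A table lists the effect detectable with 80% and 90% power at three total sample sizes. The N=30 row reads 1.06 and 1.23 SD, and the N=40 row 0.91 and 1.05 SD.

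The sample size is then taken from that table: "we will randomize 30 patients, as we hypothesize that an assumed-true effect size of 1.06 – 1.23 is achievable". Results of earlier trials are cited in support, namely "achieved effect sizes of 1.46 at 2 weeks", 1.69 at 6 weeks and 2.2 at 5 weeks. The next sentence reads "A sample size of N=30 will provide >90% power to detect a significant difference in the primary outcome" and names the two groups but no effect size.

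On numbers of participants, Section 9.2 allows for 15% drop-out, "so full enrollment in this study will be 36 with a target of 30 subjects completing the study". Section 3.1.6 says "We will recruit 30 adult participants (25 to 65 years) of both sexes". Section 2.2 describes 30 participants, and Sections 3.1.4 and 6.1 give 15 per arm.

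**The concern.** A power figure means something only at a stated effect. The only effect that the plan calls assumed-true is 1.06 to 1.23 SD, and the plan's table gives N=30 between 80% and 90% power over that range. The next sentence puts the power above 90%. Taken with the assumed range, the two statements disagree everywhere except at the very top of the range.

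The power sentence is the one most likely to be quoted in a report. Read alone, it implies a type II error below 10%. At the plan's assumed effects, with 30 analysed, that error is about 10% to 20%. A non-significant result could then be taken as stronger evidence against benefit than the design supports.

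**Working it through.** **Inputs**, all from Section 9.2 except the allocation: two-sample t-test; two-sided alpha 0.05; effect d in units of the common SD; assumed d of 1.06 to 1.23; cited earlier effects of 1.46, 1.69 and 2.2; 15 per arm (Sections 3.1.4 and 6.1).

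**Formula.** Power = P(|T| > t₀.₉₇₅,df), where T is noncentral t with df = n₁ + n₂ − 2 and noncentrality d × √(n₁n₂/(n₁ + n₂)).

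**Step 1: reproduce the table.** Solving for d at 80% and 90% power:

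| Total N | Recomputed | Plan |
|---|---|---|
| 30 | 1.060 / 1.226 | 1.06 / 1.23 |
| 40 | 0.909 / 1.052 | 0.91 / 1.05 |
| 50 | 0.809 / 0.936 | 0.81 / 0.94 |

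The table is right.

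**Step 2: power with 30 analysed.** For 15 and 15, df = 28 and the noncentrality is d × √7.5 = 2.739d.

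| d (SD) | Source | Noncentrality | Power |
|---|---|---|---|
| 1.06 | lower end of assumed range | 2.90 | 80.0% |
| 1.145 | midpoint, (1.06 + 1.23)/2 | 3.14 | 85.7% |
| 1.20 | within range | 3.29 | 88.7% |
| 1.23 | upper end of assumed range | 3.37 | 90.2% |
| 1.46 | cited trial | 4.00 | 97.1% |
| 1.69 | cited trial | 4.63 | 99.4% |
| 2.2 | cited trial | 6.02 | over 99.9% |

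Power passes 90% at d = 1.226. The type II error at the two ends of the assumed range is 100 − 80.0 = 20.0% and 100 − 90.2 = 9.8%. An uneven split of 16 and 14 barely matters: 79.8% at 1.06 and 90.0% at 1.23.

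For reference, 20 per arm gives 90.4% at 1.06 SD. This agrees with the plan's N=40 row, which is where 90% power near the lower end of the range is found.

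**Step 3: could another calculation have produced the figure?** At 1.06 SD and 15 per arm, the normal approximation gives 82.7% and a one-sided 5% t-test 88.2%. Neither exceeds 90%.

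**Step 4: if 36 were randomised and all analysed.** For 18 and 18, the noncentrality is d × √9 = 3d. Power is 87.1% at 1.06, 91.6% at 1.145 and 94.8% at 1.23; it reaches 90% at 1.112 SD. Under this scenario power is above 90% over most of the assumed range, but not at its lower end.

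**Step 5: the participant counts.** 30/(1 − 0.15) = 35.3, rounded up to 36, so the allowance is sound. Six losses of 36 is 16.7%, just above the 15% assumed. Within Section 9.2, randomising 30, enrolling 36 and having 30 complete agree only if all six losses come before randomisation. Section 6.2.1 says "randomization to the psilocybin or control (niacin) treatment groups will occur at the end of visit 2", whereas the schedule in Section 3.1 marks it at the medication visit; both come after preparation. Section 4.5 gives as a ground for withdrawal that "they miss their preparation visits without explanation". Early losses would fit these passages, but the plan does not say that this is what it expects.

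**The case against.** The best defence is that the power sentence directly follows the cited effects of 1.46, 1.69 and 2.2 SD, and at each of these N=30 gives 97% or more. On that reading 1.06 to 1.23 SD is what the design needs, the earlier trials exceeded it, and power is therefore above 90%. The reading is open, and at those effects the sentence is true. It does not remove the problem. The cited effects are offered as grounds for thinking 1.06 to 1.23 SD achievable, and the sample size is taken from that row of the table. If the larger effects were meant, the remedy is the same: name them beside the power.

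It can also be said that the consequence is small, because the correct figures stand in the table a few lines above. That is so. The risk is that the power is misquoted; nothing in the conduct or analysis of the trial changes.

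The participant counts have a defence too. The figures of 30 in Sections 2.2, 3.1.4, 3.1.6 and 6.1 agree with randomising 30, and Section 9.2 explains 36 as an allowance for drop-out. What remains is that recruiting 30 and full enrolment of 36 are not the same target.

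**Conclusion.** The power statement does not hold over the plan's own assumed range. With 30 analysed in two equal arms, the supportable statement is 80% power at 1.06 SD rising to 90% at 1.23 SD, and above 90% only for larger effects. This rests on the plan's t-test, two-sided 5% alpha and a common SD.

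Three stronger conclusions might be inferred, and the documents do not support them:

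- **That N=30 is wrong or the power table faulty.** The table reproduces, and 30 is a legitimate choice for 80% to 90% power at the stated effects.
- **That power is 80% to 90% wherever the six losses fall.** That range is for 30 analysed. The primary analysis is by intention to treat; if 36 were randomised and all analysed, the range would be 87.1% to 94.8%. Section 9.2 gives no method for missing data, so this case can be neither assumed nor excluded.
- **That 36 is an arithmetic error, or that a particular number must be the one randomised.** The 36 follows from the 15% allowance. The plan leaves open when the losses are expected, and only the sponsor can settle that.

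**What to change.** Replace the power sentence in Section 9.2 with:

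> 30 evaluable participants (15 per arm) give 80% power at a true difference of 1.06 SD and 90% at 1.23 SD; power exceeds 90% only for larger effects such as those in the cited trials (97% at 1.46 SD).

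As a minor addition, the sponsor should state in Section 9.2 whether the six losses are expected before or after randomisation, and then bring the counts in Sections 2.2, 3.1.4, 3.1.6, 6.1 and 9.2 into line with that answer. If more than 30 are to be randomised and analysed, the power should be restated for that number.

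The power change costs one sentence and makes the stated power less favourable. The sample size, test, alpha, table and drop-out allowance stay as they are.
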